Study Protocol

Review of Trend in Incidence and Characteristics of Hospital-acquired Acute Kidney Injury in Hospital Selayang

Protocol number, version number and date:

HA-AKI-1, Version 3, 1 November 2017

Name and Institution of Principal investigator:

[name], Clinical Research Centre (CRC), Hospital Selayang

Name and Institution of Co-Investigators:

[name] [name], Nephrology Department, Hospital Selayang

[name] [name], Nephrology Department, Hospital Selayang

[name], Nephrology Department, Hospital Selayang

[name], Nephrology Department, Hospital Selayang

[name] [name], CRC Hospital Pulau Pinang

[name], CRC Hospital Selayang

Name and address of Sponsor:

Self-Sponsored

Study site/s:

Hospital Selayang

Table of Contents

List of Abbreviations	3
Research Synopsis	4
1. Background and Significance	5
2. Objective.....	5
2.1 General Objective.....	5
2.2 Specific Objectives:.....	5
3. Methodology.....	6
3.1 Study Type and Design	6
3.2 Study Population	6
3.3 Inclusion Criteria.....	6
3.4 Exclusion Criteria.....	7
3.5 Withdrawal Criteria	7
3.6 Study Outcomes.....	7
3.7 Sample Size	7
3.8 Study Duration and Timeline	8
3.9 Study Visits and Procedures	8
3.10 Statistical Analysis Plan.....	8
3.11 Risk and benefit to study participants.....	8
Benefits to the participants.....	9
3.12 Risk Benefit Assessment	9
3.13 Ethics of Study.....	9
3.14 Informed Consent/Assent Process	9
3.15 Privacy and Confidentiality	9
3.16 Conflict of Interest	9
3.17 Publication Policy	9
3.18 Termination of Study	10
References.....	10

List of Abbreviations

AKI	Acute Kidney Injury
CA-AKI	Community-acquired Acute Kidney Injury
HA-AKI	Hospital-acquired Acute Kidney Injury
ICU	Intensive Care Unit
SCr	Serum creatinine

Research Synopsis

Study title	Review of Trend in Incidence and Characteristics of Hospital-acquired Acute Kidney Injury In Hospital Selayang
Study Population	Patients admitted into Hospital Selayang from: 
• 1st July 2001 to 30th June 2002• 1st July 2006 to 30th June 2007• 1st July 2011 to 30th June 2012• 1st July 2016 to 30th June 2017
Study Design	Retrospective Cohort Study
General Objective	To investigate the incidence, risk factors and outcomes of Hospital-acquired Acute Kidney Injury in Hospital Selayang over 15 years (5-yearly trend)
Specific Objectives	
• To determine the incidence pattern of Hospital-acquired Acute Kidney Injury in Hospital Selayang• To study the determinants associated with development of Hospital-acquired Acute Kidney Injury in Hospital Selayang• To describe the survival outcomes of admissions with Hospital-acquired Acute Kidney Injury, admissions with Community-acquired Acute Kidney Injury and admissions without Acute Kidney Injury in Hospital Selayang
Study endpoints/outcomes	Completion of data collection at the end of the study duration
Sample Size	170000 (minimum 11345 required)
Study Duration	1 year

1. Background and Significance

Acute kidney injury (AKI) is a common problem globally which imposed heavy illness burden to the healthcare system, especially in developing countries. (1, 2) AKI can occur in the community (termed as Community-acquired AKI (CA-AKI)) or in the hospital setting (termed as Hospital-acquired AKI (HA-AKI)). Studies have associated HA-AKI as a preventable disorder, and linked HA-AKI with several immediate and long-term outcomes adversely, such as length of hospitalization, morbidity, and residual renal function. (1, 3, 4) Moreover, delayed recovery to baseline kidney function after AKI episode is found to be associated with higher risk of adverse events and mortality. (5) The impact of HA-AKI is significantly profound, especially among HA-AKI survivors who lost their residual renal function, and remain dialysis dependent. (6)

There was an increasing trend in HA-AKI incidence among hospitalized patients.(6-8) This could be attributed to increased exposure to potentially preventable risk factors during hospitalization. (6) However, studies pertaining to Asian countries are scarce, especially Malaysia. Preventative strategies against HA-AKI could be formulated based on understanding of risk factors which could be identified earlier upon hospital admission. (4)

The purpose of this study is to compare the incidence trend of HA-AKI in Selayang Hospital for the past 15 years, as well as to determine characteristics predictive of such cases. Understanding of clinical variables associated with HA-AKI could facilitate strategies and approaches to prevent, recognize HA-AKI early and mitigate the disease burden of HA-AKI in future.

2. Objective

2.1 *General Objective*

To investigate the incidence, characteristics and outcomes of Hospital-acquired Acute Kidney Injury in Hospital Selayang over 15 years

2.2 *Specific Objectives:*

- To determine the incidence pattern of Hospital-acquired Acute Kidney Injury in Hospital Selayang
- To study the determinants associated with development of Hospital-acquired Acute Kidney Injury in Hospital Selayang

- To describe the survival outcome pattern of admissions with Hospital-acquired Acute Kidney Injury, admissions with Community-acquired Acute Kidney Injury and admissions without Acute Kidney Injury in Hospital Selayang

3. Methodology

3.1 Study Type and Design

This is a retrospective cohort study involving 5-yearly trend from 2002 to 2017 for analysis. Laboratory serum creatinine (SCr) results of all patients admitted during study period will be retrieved from the hospital Laboratory Information System. A preliminary screening list will be generated by using STATA program from the SCr results. The nephrologist will then determine HA-AKI as per inclusion and exclusion criteria. Data collectors will collect all relevant data from these patients.

[figure not shown]

Figure 1. Flow chart of the study

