3.3 Inclusion Criteria

- a) Age of 18 and above at time of hospital admission
- b) HA-AKI is defined by any patient who developed AKI (as per definition below) after 48 hours of hospital admission.
- c) Definition of AKI(9):

- i. An increase in serum creatinine of 0.3 mg/dl (26.5 μ mol/l) within 48 hours *OR*
- ii. An increase in serum creatinine to more or equal to 1.5 times baseline, which is known or presumed to have occurred within the prior 7 days

d) Definition for baseline creatinine(9):

- i. The baseline creatinine level is defined as the creatinine level at or within 7 days before the hospital admission, *OR*
 - ii. at the hospital admission *OR*
 - iii. the lowest creatinine (excluding the post dialysis creatinine if dialysis is initiated) during the index hospitalisation for those whose baseline creatinine were unknown.

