3.7 Sample Size

The primary outcome of interest is development of HA-AKI during admission at our centre. The incidence of Hospital-acquired AKI at our centre at March 2017 was 1.19% based on one ongoing study (A prospective, multicenter, observational study to determine the incidence and outcome of Acute Kidney Injury among hospitalised patients in Malaysia). The nine variables to be investigated for predictors of HA-AKI are age, gender, ICU

admission, race, nephrotoxin use, diabetes mellitus, hypertension, congestive heart failure and chronic obstructive pulmonary disease. With an estimation of 15 events per predictor, a minimum of 135 events would be needed, translating to a minimal of 11345 patients at our centre required for the study. The study population fits the minimum sample size requirement as 170283 adult admissions were recorded in total (22788 for Year 2002, 41731 for Year 2007, 46330 for Year 2012 and 59434 for Year 2017).

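### ICU admission and nephrotoxin use enter the HA-AKI determinants model with no pre-onset exposure window and no at-risk comparator group

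*Combined protocol and SAP*

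**What the plan says.** Section 3.7 names the candidate predictors: "The nine variables to be investigated for predictors of HA-AKI are age, gender, ICU" and, continuing, "admission, race, nephrotoxin use, diabetes mellitus, hypertension, congestive heart failure", with chronic obstructive pulmonary disease as the ninth. ICU admission and nephrotoxin use appear as bare names. Section 3.10 adds that risk factors will be related to a categorical outcome by multiple logistic regression. It gives no timing and no comparison group.

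Section 3.3 sets when the outcome can occur: "HA-AKI is defined by any patient who developed AKI (as per definition below) after 48 hours of hospital admission". No upper limit is given.

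On data collection, 3.1 first says "Laboratory serum creatinine (SCr) results of all patients admitted during study period will be retrieved from the hospital Laboratory Information System". After a screening list is generated, it continues: "The nephrologist will then determine HA-AKI as per inclusion and exclusion criteria. Data collectors will collect all relevant data from these patients".

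Section 1 gives the purpose of the determinants analysis: "to determine characteristics predictive of such cases". It adds: "Preventative strategies against HA-AKI could be formulated based on understanding of risk factors which could be identified earlier upon hospital admission". It also offers an explanation for rising incidence: "This could be attributed to increased exposure to potentially preventable risk factors during hospitalization".

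**The concern.** A determinant has to come before the outcome. Seven of the nine predictors (age, gender, race and four chronic conditions) are normally fixed or known at admission, so their timing is not in doubt. ICU admission and nephrotoxin use are events within the stay and can start before or after AKI. Someone abstracting from the text as written could properly record ICU as yes for a patient moved there because of the AKI. That entry would then count towards ICU admission as a predictor of AKI.

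These two predictors also matter most for the stated purpose, since they are the in-hospital exposures on the list. If they absorb the consequences of AKI, the model no longer answers the predictive question posed in section 1.

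The comparator group raises a linked problem. By the 3.3 definition, an admission that ends before 48 hours cannot become HA-AKI. It also has less time to enter ICU or receive a nephrotoxin. Using such admissions as comparators tends to lower comparator exposure and raise both odds ratios for reasons unrelated to risk.

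**Working it through.** **The plan's own figures.** 15 events × 9 predictors = 135 events. 135 / 0.0119 = 11,344.5, rounded up to 11,345, as stated in 3.7. The yearly counts give 22,788 + 41,731 + 46,330 + 59,434 = 170,283, also as stated. The sample size arithmetic is correct, and this point does not affect it.

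**Search for a window.** Section 3.7 names the two exposures, 3.10 names the regression, 3.3 dates the outcome as after 48 hours, and 3.1 asks for all relevant data. None of these limits exposure to the time before onset, and none sets a period for admissions without AKI. No other section does either.

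**Direction of the bias.** The exposure rates below are assumptions; the documents give none. Let

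- b = proportion exposed before the index time, equal in cases and non-cases, so the true odds ratio is 1;
- q = later exposure among the remaining cases;
- r = later exposure among the remaining non-cases.

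Coded as any exposure in the stay, the apparent odds ratio is odds(b + (1 − b)q) / odds(b + (1 − b)r). It exceeds 1 if q > r and falls below 1 if q < r.

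| Exposure | b | q | r | Exposed, cases | Exposed, non-cases | Apparent OR |
|---|---|---|---|---|---|---|
| ICU | 0.05 | 0.10 | 0.05 | 0.145 | 0.0975 | 1.57 |
| ICU | 0.05 | 0.20 | 0.05 | 0.240 | 0.0975 | 2.92 |
| Nephrotoxin | 0.30 | 0.10 | 0.05 | 0.370 | 0.335 | 1.17 |
| Nephrotoxin | 0.30 | 0.20 | 0.05 | 0.440 | 0.335 | 1.56 |
| Nephrotoxin | 0.30 | 0.02 | 0.10 | 0.314 | 0.370 | 0.78 |

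The last row represents nephrotoxins being withheld once AKI is recognised. If non-cases are assumed to have no later ICU entry (r = 0), with b from 0.03 to 0.10 and q from 0.05 to 0.20, the ICU values run from 1.53 (b = 0.10, q = 0.05) to 9.33 (b = 0.03, q = 0.20). The spread shows how far the result depends on unknown rates.

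**A one-sided correction is not enough.** If cases are cut off at onset (q = 0) but comparators are counted over the whole stay, the first ICU row becomes (0.05/0.95) / (0.0975/0.9025) = 0.0526 / 0.1080 = 0.49. The window has to be the same in both groups.

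**A large sample does not help.** If 1.19% held in all four periods (3.7 reports it only for March 2017), 170,283 × 0.0119 gives about 2,026 cases and 168,257 non-cases. For the first ICU row, the expected counts are about 294 exposed and 1,732 unexposed cases, and 16,405 exposed and 151,852 unexposed non-cases. The standard error of the log odds ratio is √(1/294 + 1/1,732 + 1/16,405 + 1/151,852) ≈ 0.064. The 95% interval is exp(0.451 ± 1.96 × 0.064), about 1.39 to 1.78. It excludes the true value of 1, so the spurious association would pass the 0.05 rule in 3.10.

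**The case against.** The strongest reply is that the objective in 2.2 speaks of determinants of the development of HA-AKI, which signals that earlier exposure is intended, and that a design overview is not where variable definitions belong. The first part is fair as to intent, but no section turns that intent into a rule for abstraction. The second is a reason to put the rule in 3.7 and 3.10.

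It can also be said that the illustration rests on invented rates. That stands: only the existence of the bias and what governs its direction are established.

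A first-48-hours window also has limits. Section 1 points to exposures during the stay, and such a window drops those arising between 48 hours and onset. Precedence is not perfectly clean either. Section 3.3 allows a rise presumed to have occurred within the prior seven days, and a baseline taken as the lowest in-stay creatinine, so injury may begin before it is detected. This argues for stating the chosen window and its limits. It does not argue for leaving the window open.

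A reader might go further and infer from 3.1 that covariates are collected for HA-AKI cases only, so that the regression has no comparators. The documents do not support that. The design is called a cohort study, the synopsis gives a sample size of 170,000, 3.7 counts 170,283 admissions, and the 11,345 is a number of patients obtained from 135 events, which makes sense only if non-cases are in the model. Figure 1, not shown in the text reviewed, may state it outright.

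**Conclusion.** The point holds for the exposure window and the at-risk group. As written, the plan allows post-onset ICU care and nephrotoxin use to be counted as determinants of HA-AKI, which would bias two of the nine odds ratios. For ICU admission the bias is probably upward, if AKI itself leads to ICU transfer. For nephrotoxins it could go either way. Its size cannot be derived from the documents, and the figures above show only that moderate assumed rates are enough to produce a clear false association.

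The damage is confined to the determinants objective. HA-AKI incidence, renal recovery and in-hospital mortality do not depend on exposure timing. The conclusion assumes that the two variables would be coded as any exposure during the admission, which the text permits but does not state. It should be fixed before abstraction starts, because undated yes/no entries can be corrected only by reopening records.

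Whose covariates are collected is a matter of wording. It is not evidence that comparators are absent.

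**What to change.** - In 3.7 and 3.10, count ICU admission and nephrotoxin use only if they begin before AKI onset, and record their start dates. Sections 3.6 and 3.10 already need a date of AKI diagnosis for the mortality and survival analyses, so the same date can mark onset.
- Apply the same window to comparators. Either use the first 48 hours for everyone, or use exposure up to onset with a matched index time in comparators. Name one as the main analysis. The first is simpler and fits the aim of early identification. The second keeps later in-hospital exposure, but the analysis must then respect the matching on index time.
- Restrict the determinants model to admissions still in hospital and AKI-free at 48 hours. By the 3.3 definition HA-AKI arises only after that point, so this should cost no cases. The number of comparators lost cannot be given, because the documents report no lengths of stay.
- As a minor clarification, say in 3.1 that the patients whose data are collected include the non-cases used in the model, unless Figure 1 already does.

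The cost is protocol wording plus abstraction of exposure dates. Logistic regression can remain the method. The main loss, under a 48-hour window, is pre-onset exposure that begins later than 48 hours, and the report should say so.

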3.8 Study Duration and Timeline

Proposed study will be conducted from 1 November 2017- 1 November 2018 in the stages shown below:

- Stage 1, review of medical records – 5 months
- Stage 2, data collection and data analysis –5 months
- Stage 3, presentation and publication – 2 months

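### HA-AKI is settled by a nephrologist's call with no stated masking, review order or rule-only analysis, so calls that differ by period or exposure could bias both the 15-year trend and the determinants.

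*Combined protocol and SAP*

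**What the plan says.** Section 3.1 gives a sequence. Creatinine results are retrieved from the laboratory system and "A preliminary screening list will be generated by using STATA program from the SCr results". Next, "The nephrologist will then determine HA-AKI as per inclusion and exclusion criteria". Then "Data collectors will collect all relevant data from these patients".

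Section 3.7 makes this determination the main endpoint: "The primary outcome of interest is development of HA-AKI during admission at our centre". The same variable is the outcome for nine candidate predictors, among them ICU admission and nephrotoxin use.

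Section 3.3 supplies the criteria. The thresholds are numeric, but three elements call for judgement:

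- The 1.5-fold rise is one "which is known or presumed to have occurred within the prior 7 days".
- Baseline has three alternatives joined by OR. The last is the lowest value (post-dialysis values excluded) "during the index hospitalisation for those whose baseline creatinine were unknown".
- Hospital-acquired status depends on dating onset: "HA-AKI is defined by any patient who developed AKI (as per definition below) after 48 hours of hospital admission".

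Section 3.8 sets aside five months for a first stage called "review of medical records", ahead of data collection and analysis. Neither section 3.1 nor the analysis plan in section 3.10 mentions masking, the order of review, the number of readers, an agreement check or an analysis that uses the creatinine rule alone. The flow chart (Figure 1) is not reproduced in the text available for this review, so any process detail in it could not be checked.

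**The concern.** One human determination feeds two comparisons: incidence across the four periods, and the regression of HA-AKI on ICU admission, nephrotoxin use and the other predictors. If borderline candidates are accepted more readily in one period, or more readily when the patient was in ICU or on a nephrotoxin, that difference appears in the results as a trend or an odds ratio. A reader whose standard drifts during the review would have the same effect if records are read period by period, and the plan fixes no order that would prevent this.

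The Background (section 1) already reports rising HA-AKI incidence and suggests in-hospital exposures as a cause. That does not show that calls will be biased, but it means that a reader aware of period and exposure would have an expected direction. Large numbers do not help: 170283 admissions reduce random error, not differential classification, and they allow a modest artefact to reach p<0.05.

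**Working it through.** **Inputs from the documents (sections 3.7 and 3.10).** Incidence 1.19%; nine predictors at 15 events each; 22788, 41731, 46330 and 59434 admissions in the four periods; two-sided 0.05.

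**The plan's own figures.** 9 × 15 = 135 events; 135 / 0.0119 = 11344.5, rounded up to 11345. The four periods sum to 170283. Both agree with section 3.7, and neither is in dispute.

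**Expected cases at 1.19% in every period (assumption).** About 271, 497, 551 and 707; total about 2026.

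**Smallest significant difference, first v last period.** Section 3.10 names no specific test for comparing periods, so a two-proportion comparison stands in, with the variance taken at 1.19% in both.

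SE = √[0.0119 × 0.9881 × (1/22788 + 1/59434)] = 0.0845 percentage points. 1.96 × SE = 0.166 points, and 0.166 / 1.19 = 13.9% relative.

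**Chance of a false significant result with no true change.** The relative drift in calls, 2017 over 2002, is assumed. The pairwise column is Φ[(Δ − 1.96 × SE pooled) / SE unpooled]. The last column is a normal-approximation Cochran-Armitage test with the drift spread linearly over the four periods.

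| Drift | Apparent 2017 incidence | Extra cases in 2017 | 2017 v 2002 | Four-period trend |
|---|---|---|---|---|
| 5% | 1.25% | 35 | 10% | 12% |
| 10% | 1.31% | 71 | 27% | 34% |
| 15% | 1.37% | 106 | 52% | 62% |
| 20% | 1.43% | 141 | 76% | 85% |
| 30% | 1.55% | 212 | 98% | 99% |

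**How uneven would the calls have to be?** Let a share b of candidates be borderline, accepted at rate a₁ in one period and a₂ in another. The incidence ratio is (1 − b + b·a₁) / (1 − b + b·a₂). All values of b and a are assumptions.

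- b = 20%, 60% v 40%: 0.92 / 0.88 = 1.05
- b = 20%, 70% v 30%: 0.94 / 0.86 = 1.09
- b = 30%, 70% v 30%: 0.91 / 0.79 = 1.15

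Only the last exceeds the 13.9% threshold.

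**Determinants.** For one binary exposure with true odds ratio 1, unadjusted, at 30% prevalence (assumption), the SE of the log odds ratio is about √[1/(0.3 × 2026) + 1/(0.7 × 2026)] = 0.0485. The smallest significant odds ratio is therefore exp(1.96 × 0.0485) = 1.10. If calls run 10% higher in the exposed, the odds ratio is about 1.10 and the chance of p<0.05 about 53% (28% to 60% for prevalence 10% to 50%). At 20% higher it is about 1.20 and 98% (75% to 99%).

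**The case against.** The strongest objection is that the documents never say what the nephrologist sees. A reader might infer a reviewer who has the admission year, ICU stay and drug chart open, with work divided among reviewers by period. The text does not establish this. Section 3.1 says only that the criteria are applied, refers to the nephrologist in the singular, and places data collection afterwards in other hands. Section 3.8 does not tie its record-review stage to this call. Access to the dated record is plausible, because the 48-hour rule needs admission and sample times and the exclusion of end-stage renal failure or renal replacement therapy (ESRF/RRT) needs clinical facts. It remains an inference, and is weakest for drug exposure.

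Discretion is also limited. The thresholds are numeric and a program chooses the candidates. If only listed cases are judged, the nephrologist can only remove them. That narrows the room for error, but unequal removal by period or exposure would still bias both comparisons.

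A further tempting step is to let the STATA rule replace the nephrologist. The definition does not allow this on creatinine values alone: the baseline fallback excludes post-dialysis values, which needs dialysis information.

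All of these objections stand. They rule out saying that bias will occur, and they rule out discarding the reviewed outcome. They do not supply a safeguard that the plan lacks.

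**Conclusion.** The point holds as a weakness of design, not as a demonstrated bias. The primary outcome depends on a judgement that the plan neither masks nor sets beside a fixed rule, and that outcome carries both main analyses. Whether calls would differ by period or exposure is unknown, and the documents give no figure from which to estimate it.

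The illustration gives the scale only. A spurious relative difference of about 14% between the first and last periods would be significant, while 5% usually would not. For a common exposure an odds ratio of 1.10 is enough. These figures rest on a constant 1.19% incidence, independent admissions, no true effect, and assumed drift, borderline shares and exposure prevalence. The change is worth making because it is cheap and would let readers see whether judgement moved the results.

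**What to change.** Keep the nephrologist's determination and add two things to sections 3.1 and 3.10.

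1. **A rule-based analysis.** Write one fixed creatinine rule in advance, covering choice of baseline, timing of the rise and onset relative to 48 hours. Run it in STATA identically on all four periods. Apply the same ESRF/RRT exclusion as in the reviewed analysis, and flag post-dialysis values during that check. Report the rule-based incidence trend and determinants model beside the reviewed ones.
2. **Masked, shuffled review.** Present listed cases as creatinine series by hospital day, in random order across the four periods. Withhold calendar year, ICU and drug data until the call is recorded. Open the full record for unclear series only after that, and keep both calls.

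The cost is some STATA work to build the sheets, a second look at unclear series, and exposure data for rule-positive candidates whom the nephrologist rejects. The creatinine data are already being retrieved, and no extra reviewers are needed. Masking will be partial, because ESRF/RRT and dialysis status require the record, and the first call is made with less clinical context.
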